Amended version 11:	10/31/2019	Updated sub-investigators and changed Lead Study Coordinator on p.1; Rationale for

Amendment Version 08/19/2020
12

expanding the eligible age to a younger patient population added to Section 7.3. Rewording in Section 7.2.4. Clinical experience background information updated in Section 7.2.6. Magnevist® co-infusion removed from study, along with corresponding immediate post-infusion MRI affecting Sections 5.3, 9.1.2, 9.1.3, 11.2, and 12.3 and Table 2. Sentence removed from Section 9.1.3.

Sentence describing risks of sedation added in Section 9.1.6; Age range changed in Section 9.2 and in inclusion criteria in Section 11.1. Inclusion criterion regarding ability to undergo brain MRI without anesthesia removed in Section 11.1. Clarified assent in inclusion criteria in Section 11.1; Exclusion criterion regarding previous PV infection reworded in Section 11.2; Exclusion criterion regarding gadolinium allergy changed in Section 11.2; Remove KPS on Day 1 in Section 12, Table 2 and Section 12.4; Add a 4 mL blood draw for immune analysis on Day 1 in Section 12, Table 2 and Section 12.4; Baseline MRI within 3 days changed to within 5 days in Table 2 and Section 12.1; Text in Section 13.1.1 changed to N/A.

Cover page: updated CMO for Istari. Updated language to remove 14-day hold between treated patients based on interim safety review in Sections 5.5, 7.3, and 15.4.1. Clarified Sponsor monitoring in Section 14.1.

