5.5 Data Analysis and Statistical Considerations

[figure not shown]
A maximum of 12 patients will be treated with PVSRIPO, and then carefully monitored for safety for at least a year after treatment. Of particular interest will be the incidence of adverse events that occur during the first 14 days after PVSRIPO treatment and the inflammatory events that occur during the first year after PVSRIPO treatment. Our experience with PVSRIPO treatment of adult patients with recurrent WHO grade IV malignant glioma suggests that a patient remains at risk, during the first 12 months post-PVSRIPO treatment, of demonstrating neurologic or radiographic signs suggestive of an inflammatory reaction secondary to the immune response triggered by PVSRIPO that requires a dose of dexamethasone above 4 mg a day. As described in Section [9.1.6](#), such patients will be treated with bevacizumab 7.5 mg/kg IV every 3 weeks if possible, or alternatively corticosteroids or surgery.

The accrual of pediatric patients to this study was staggered for the first 5 patients enrolled so that no more than 1 patient was treated every 14 days. A slow accrual was planned to minimize the number of pediatric patients exposed to PVSRIPO before adequate information about the sequelae of the inflammatory process within a pediatric patient is known. Based on a review of the available safety data and acceptable tolerability in the first 5 patients treated with PVSRIPO (no dose-limiting toxicities or suspected unexpected serious adverse reactions observed), the protocol was amended to allow for accrual of subsequent patients without the 14-day waiting period in Protocol Amendment 12.

Two sets of safety monitoring guidelines are proposed in Section [15.4.1](#), with one focused on acute toxicity (i.e. occurring during the first 14 days after PVSRIPO administration), and one focused on long-term issues.

The Kaplan-Meier estimator will describe the survival of patients treated with PVSRIPO. Survival (OS) will be calculated as the time between PVSRIPO infusion and death, or last follow-up if the patient remains alive. Analyses will be stratified by grade.

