The Food and Drug Administration (FDA) recommended that the pediatric trial initially enroll patients 12 years of age and older and up to and including 18 years of age. We are including a number of WHO grade III and IV malignant brain tumor histologies and tumor locations in this trial. Specifically, eligible patients may include patients with recurrent WHO Grade III gliomas, such as anaplastic astrocytoma, anaplastic oligoastrocytoma, anaplastic oligodendrogloma, anaplastic pleomorphic xanthoastrocytoma, or ependymoma, as well as patients with WHO Grade IV gliomas, including glioblastoma or gliosarcoma. CD155 is avidly expressed in medulloblastoma, atypical teratoid rhabdoid tumor (ATRT), and embryonal tumors ²⁶, so these histologies will be included here as well.

Given that the incidence of embryonal tumors, ependymoma, and glioma peaks at ages lower than the initial eligible age for this clinical trial (≥ 12 years old), the study has experienced relative challenges to enrollment during its first two years. The incidence of the aforementioned tumor types is higher in younger children approximately 5 to 9 years of age and then continuously falls after 9 years old to a nadir in early adulthood ^{27,28}. In addition, the biology of brains in children aged 4 to 11 and the biology of the predominant types of brain tumors seen in this age range (i.e., glioma, ependymoma, and medulloblastoma) are similar to that of children who are 12 and over ¹. Tumors in children younger than 4 years old tend to have different genotypes and thus behave differently than tumors in children older than 4 years old ¹. There are currently active pediatric clinical trials in the US investigating the use of different oncolytic viruses, such as herpes simplex virus-1 (HSV-1) (NCT03911388 and NCT02451845) and a modified measles virus (NCT02962167), in a similar pediatric population. These trials also deliver the oncolytic virus via intratumoral administration and

include a population of children ranging in age from 3 to 18 years old in the case of aforementioned HSV-1 trial and children and adults ranging in age from 1 to 39 years old in the case of the modified measles virus.

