MRI imaging, within 4 hours of the completion of infusion, was registered to define the shape and position of the contrast agent distribution relative to the patient’s brain anatomy in patients treated prior to October 31, 2019. Because enrollment criteria for these patients was limited to patients aged \geq 12 years old, sedation was not required for the MRI. While gadolinium-diethylene triamine pentaacetic acid (Gd-DTPA) is a widely available MRI contrast agent, there has been speculation that its small molecular weight (938 Dalton) could limit its ability to predict the distribution of the larger molecules typically infused therapeutically with CED [reviewed in Reardon et al., 2011 ³⁰]. Development of large molecule tracers labeled with gadolinium (Gd) has been problematic, but it has been stipulated that infusion of low molecular weight Gd-DTPA can predict the distribution of larger molecules by systematic post-infusion manipulation of the images based on theoretical differences in the predicted distribution of the Gd-DTPA and the therapeutic drug being infused ³¹. This has been confirmed by simultaneously infusing a patient with a supratentorial recurrent malignant glioma with an epidermal growth factor receptor (variant III) (EGFRvIII)-targeted immunotoxin in combination with ¹²⁴I-human serum albumin (HSA) [to permit positron emission tomography (PET) imaging] and Gd-DTPA. Gd-DTPA co-infusion provided direct information about the distribution of large molecules with high resolution ³¹. In combination with fluid-attenuated inversion recovery (FLAIR) imaging, Gd-DTPA co-infusion provides additional information about leak into cerebrospinal fluid spaces and resection cavities ³².

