9.2 Rationale for Selection of Dose, Regimen, and Treatment Duration

Dose: The dose for this trial was selected based on IND-directed toxicity studies ²⁵ and on experience from an ongoing study in adults with recurrent WHO grade IV malignant glioma. Dose-range finding and toxicity studies in non-human primates documented the absence of viral encephalomyelitis, poliomyelitis and meningitis with intracerebral injection of PVSRIPO up to a dose of 5×10^9 TCID50 ²⁵. In the adult WHO grade IV malignant glioma study, 4 patients were dosed at the maximum dose of 1×10^{10} TCID50 without signs of viral encephalomyelitis, poliomyelitis or meningitis. Given that the brain size of the target population for this trial (children and young adults aged 4-21) is nearly identical to that of adults, and that the human brain is ~10-times the size of the primate species used in the IND-directed toxicity studies (*M. Fascicularis*), the dose of 5×10^7 TCID50 in this trial is 500-times below the maximum feasible safe dose in *M. Fascicularis* and 1000-times below the maximum dose in the adult WHO grade IV malignant glioma study. The proposed dose of 5×10^7 TCID50 corresponds to the dose selected for future studies based on the Phase I adult WHO grade IV malignant glioma study. If unacceptable toxicity that requires dose reduction occurs, according to Section 15.4.1, we may consider a PVSRIPO dose reduction to 3.3×10^6 TCID50.

Regimen and Treatment Duration: The treatment regimen for PVSRIPO is single intracerebral infusion, as in the ongoing adult WHO grade IV malignant glioma study.

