11 SUBJECT ELIGIBILITY

11.1 Inclusion Criteria

1. Patients must have a recurrent supratentorial WHO Grade III malignant glioma (anaplastic astrocytoma, anaplastic oligoastrocytoma, anaplastic oligodendrogloma, anaplastic pleomorphic xanthoastrocytoma, ependymoma) or WHO Grade IV malignant glioma, medulloblastoma, or atypical teratoid/rhabdoid tumor (ATRT) based on imaging studies with measurable disease (≥ 1 cm and ≤ 5.5 cm).

- a. The prior histopathology must be consistent with a World Health Organization (WHO) Grade III or IV malignant tumor confirmed by the study pathologist, [name], or his designee.
- b. The tip of the infusion catheter can be placed \geq 1cm from any ventricle.
- 2. There is no standard of care treatment for children with Grade III/IV gliomas; however, patients must have received some form of definitive treatment, i.e., standard therapy with known clinical benefit, for their initial diagnosis prior to their recurrence/progression. Definitive treatment includes maximal safe resection (if possible) and radiation therapy with or without chemotherapy. (*Please note that patients who are unable to receive radiation therapy due to genetic disorders that put them at significant risk for radiation-induced secondary malignancies (i.e., Gorlin's syndrome or NF1 mutation) are still eligible to participate.*)
- 3. All patients must be \geq 4 years of age and \leq 21 years of age at the time of entry into the study.
- 4. The patient must have a Lansky or Karnofsky Performance Score (KPS) of \geq 70% at the time of entry.
- 5. Laboratory Studies:
 - a. Platelet count \geq 125,000/ μ l prior to biopsy. Platelets \geq 100,000/ μ l prior to infusion;
 - b. Prothrombin and Activated Partial Thromboplastin Times \leq 1.2 x upper limit of normal (ULN) prior to biopsy;
 - c. Positive serum anti-poliovirus titer \geq 1:8 prior to biopsy;
 - d. Creatinine \leq 1.2 x ULN prior to biopsy;
 - e. Total bilirubin, AST, ALT, alkaline phosphatase \leq 2.5 x ULN prior to biopsy;
 - f. Neutrophil count \geq 1000 / μ l prior to biopsy;
 - g. Hemoglobin \geq 9 gm/dl prior to biopsy (can be transfused).
- 6. The patient must have received a boost immunization with trivalent inactivated IPOL™ (Sanofi-Pasteur) \geq 1 week prior to administration of the study agent.
- 7. At the time of biopsy, prior to administration of virus, the presence of recurrent tumor must be confirmed by histopathological analysis.

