15.4.1 Overview of Study Design and Monitoring

Patients will be treated with PVSRIPO, then carefully monitored for safety for at least 1 year after treatment. Of particular interest will be the incidence of AEs that occur during the first 14 days after PVSRIPO treatment and the inflammatory events that occur during the first year after PVSRIPO treatment. The experience with PVSRIPO treatment of adult patients with recurrent WHO grade IV malignant glioma suggests that a patient remains at risk, during the first 12 months post-PVSRIPO treatment, of demonstrating neurologic or radiographic signs suggestive of an inflammatory reaction secondary to the immune response triggered by PVSRIPO that requires a dose of dexamethasone above 4 mg a day. As described in Section 9.1.6, such patients will be treated with bevacizumab 7.5 mg/kg IV every 3 weeks if possible, or alternatively corticosteroids or surgery.

Two sets of safety monitoring guidelines are proposed, with one focused on acute toxicity (i.e. occurring during the first 14 days after PVSRIPO administration), and one focused on long-term issues.

Acute Toxicity Monitoring Guidelines: Monitoring rules based upon the occurrence of an unacceptable toxicity, as defined in Section 9.1.5, during the first 14 days after PVSRIPO administration are shown below in **Table 4**.

If the number of patients with an unacceptable toxicity surpasses the noted thresholds, accrual will be suspended. Data will be carefully reviewed to determine if accrual should be terminated, continued without modification, or continued with appropriate modification (e.g. PVSRIPO dose reduction).

Table 4. Acute Toxicity Monitoring Rules.

# of Patients Accrued	Accrual Suspension Threshold
0 – 6	≥2 patients with unacceptable toxicity
7-9	≥3 patients with unacceptable toxicity
10-12	≥4 patients with unacceptable toxicity

The probability of study suspension and the expected number of treated patients before study suspension is tabulated below in **Table 5** as a function of the true underlying probability of an unacceptable toxicity.

Table 5. Probability of study suspension.

True Underlying Probability of a Unacceptable Toxicity within 14 days of PVSRIPO administration	Probability of Accrual Suspension	Expected Number of Patients to be Accrued
0.05	0.030	11.8
0.10	0.124	11.1
0.15	0.262	10.2
0.20	0.411	9.2
0.25	0.560	8.1
0.30	0.681	7.2
0.35	0.792	6.2
0.40	0.873	5.4

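### Eligibility was widened mid-trial from 12-18 to 4-21 years, but Table 4 keeps one all-age count, so event-free older patients raise the number of toxicities tolerated among 4-11-year-olds

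*Combined protocol and SAP*

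**What the plan says.** **Age range.** Section 7.3 records that the FDA "recommended that the pediatric trial initially enroll patients 12 years of age and older and up to and including 18 years of age". Inclusion criterion 3 in Section 11.1 now runs from 4 years to "21 years of age at the time of entry into the study", and Section 9.2 describes the target population as "children and young adults aged 4-21". The version 11 entry in the amendment log (10/31/2019) refers to a rationale for "expanding the eligible age to a younger patient population added to Section 7.3". Section 9.1.3, on patients treated before 31 October 2019, explains why they needed no sedation: "Because enrollment criteria for these patients was limited to patients aged" 12 or more.

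**Monitoring rule.** Section 15.4.1 states "If the number of patients with an unacceptable toxicity surpasses the noted thresholds, accrual will be suspended". Table 4 sets the threshold at 2 or more patients with unacceptable toxicity for 0-6 accrued, 3 or more for 7-9, and 4 or more for 10-12. Its only index is total patients accrued. Table 5 gives the suspension probability for one true toxicity rate that applies from patient 1 to patient 12.

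**Results so far.** Section 5.5 drops the 14-day wait between patients "Based on a review of the available safety data and acceptable tolerability in the first 5 patients treated with PVSRIPO", among whom it reports no dose-limiting toxicities. The wait is dropped for all later patients, with no age condition.

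**Age in the analysis.** Sections 15.4.1, 15.8 and 15.9 contain no age-specific count, threshold or operating characteristic. Section 15.4.2 plans no toxicity summary by age.

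**The concern.** The Table 4 threshold rises as patients accumulate because each event-free patient is evidence that the common toxicity rate is low. That reasoning needs the earlier patients to be informative about the later ones. Once 4-11-year-olds became eligible, event-free patients aged 12 or over counted as evidence about a group that had not yet been treated.

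Suppose the first five patients were all 12 or older and event-free, and patients 6 and 7 are younger children who both have an unacceptable toxicity. At patient 6 there is one event against a threshold of 2. At patient 7 there are two events against a threshold of 3. Accrual continues although both younger children treated were affected.

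Safety of the selected dose in children is the primary objective, and the documents report no toxicity experience at this dose for ages 4-11 separately. The pre-specified rule is least sensitive in the group most recently added.

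**Working it through.** **Inputs.** Thresholds are from Table 4, the maximum of 12 patients from Section 15.9, and the true rates from the rows of Table 5. Two inputs are assumptions: m, the number of event-free patients aged 12 or over treated first, and that the remaining 12-m patients are all aged 4-11.

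**Step 1: reproduce Table 5.** Patients enter one at a time with toxicity probability p. The distribution of cumulative events is updated after each patient, and accrual stops when the count reaches 2 (n = 1-6), 3 (n = 7-9) or 4 (n = 10-12).

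| True rate | Suspension, recomputed | Table 5 | Expected N, recomputed | Table 5 |
|---|---|---|---|---|
| 0.05 | 0.035 | 0.030 | 11.75 | 11.8 |
| 0.10 | 0.128 | 0.124 | 11.11 | 11.1 |
| 0.20 | 0.408 | 0.411 | 9.19 | 9.2 |
| 0.30 | 0.686 | 0.681 | 7.15 | 7.2 |
| 0.40 | 0.872 | 0.873 | 5.45 | 5.4 |

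Table 5 is sound for its own assumption of one common rate. Section 15.4.1 speaks of surpassing a threshold, while Table 4 uses at-least signs. Only the at-least reading reproduces Table 5 (the stricter one gives 0.655 at 0.40), so it is used here.

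**Step 2: pooled rule after m = 5.** The seven younger children are patients 6-12. One event in the first child cannot suspend. Children 2-4 face a threshold of 3, and children 5-7 a threshold of 4. So

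P(suspend) = P(at least 4 of 7) + P(exactly 3 of the first 4) × P(0 of the last 3).

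- At 0.30: 0.1260 + 0.0756 × 0.343 = 0.152.
- At 0.40: 0.2898 + 0.1536 × 0.216 = 0.323.

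**Step 3: Table 4 also counted afresh for those seven.** A seventh child cannot bring the count from 1 to 3, so this is P(at least 2 of 6) = 1 - (1-p)^6 - 6p(1-p)^5.

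- At 0.30: 1 - 0.1176 - 0.3025 = 0.580.
- At 0.40: 1 - 0.0467 - 0.1866 = 0.767.

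The fresh count is never looser than the pooled one in these cases, so adding it to the overall rule gives the same figures.

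**Step 4: range over m** (pooled v added separate count).

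| m | Rate 0.30 | Rate 0.40 |
|---|---|---|
| 1 | 0.601 v 0.662 | 0.812 v 0.850 |
| 2 | 0.499 v 0.648 | 0.729 v 0.835 |
| 3 | 0.385 v 0.648 | 0.617 v 0.835 |
| 4 | 0.264 v 0.607 | 0.478 v 0.797 |
| 5 | 0.152 v 0.580 | 0.323 v 0.767 |

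**Step 5: without conditioning on event-free patients.** Take five older patients at an assumed rate of 0.05, then seven younger ones. The older patients have 0, 1 or at least 2 events with probability 0.7738, 0.2036 and 0.0226. At a younger rate of 0.30, the pooled rule suspends with probability 0.152, 0.524 and 1 in these cases:

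0.7738 × 0.152 + 0.2036 × 0.524 + 0.0226 = 0.247.

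With the added count the case probabilities are 0.580, 0.630 and 1:

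0.7738 × 0.580 + 0.2036 × 0.630 + 0.0226 = 0.600.

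At 0.40 the same calculation gives 0.417 v 0.778.

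**The case against.** **Comparison with Table 5.** A reader might set 0.152 beside Table 5's 0.681 and infer that the rule is far weaker than the plan states. The documents do not support that. Table 5 gives pre-trial probabilities for 12 patients, whereas 0.152 is conditional on five event-free patients with seven to come. A single age group with a common rate of 0.30 would also give 0.152 at that stage, as any cumulative rule would show such a fall. The valid contrast is pooled against separate count in the same children, and there the gap remains.

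**Who the first five were.** A reader might also infer that they were all 12 or older. Section 9.1.3 covers only patients treated before 31 October 2019 and gives no number. The review of five patients belongs to Amendment 12, after the widening, so some may have been under 12. Nor is it stated that they had no Table 4 events. Section 5.5 speaks of dose-limiting toxicities, while Section 9.1.5 defines unacceptable toxicity, which includes Grade 2 or higher autoimmune events and Grade 3 or higher surgical complications. Both objections stand, which is why a range is shown. At m = 1 the loss is small.

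**Pooling was reasoned.** Section 7.3 argues that brain and tumour biology at 4-11 resembles that at 12 and over, and Section 9.2 that brain size is nearly that of adults. Part of the Section 7.3 text was not available here and may say more. This supports eligibility and makes pooling defensible, but it is not toxicity data by age.

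**Other safeguards.** The DSMB-Plus can recommend stopping (13.7), adverse events are reviewed periodically (13.1.2), serious events reach the sponsor within 24 hours (13.2.1), and one irreversible inflammatory reaction interrupts enrolment (15.4.1). These are real protections, and Table 4 only triggers a review. None has an age-specific trigger.

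**Conclusion.** The point holds in a bounded form. Table 4 lets event-free older patients raise the number of unacceptable toxicities tolerated among 4-11-year-olds, and Table 5 does not describe monitoring of that group. At a true rate of 0.30 in the younger children, the pooled rule loses 0.06 in suspension probability against an added separate count when m = 1, 0.26 when m = 3 and 0.43 when m = 5. Without conditioning, the gap is 0.247 v 0.600.

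This rests on m event-free older patients being treated first and on all later patients being 4-11. Ages 12-21 remain eligible, so further event-free older patients would weaken the rule more: with eight of them first and four younger after, suspension at 0.40 is 0.026 v 0.525. The plan names no unacceptable rate, so 0.30 and 0.40 are illustrative rows of Table 5. The documents do not show that Table 5 is wrong on its own terms, that toxicity differs by age, or that younger children have been harmed.

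**What to change.** - In Section 15.4.1, keep the overall rule and add that the Table 4 thresholds are also applied to patients aged 4-11, counted from the first such patient treated. Reaching a threshold on that count pauses accrual of that age group for data review.
- Beside Table 5, add the operating characteristics of the two counts together, using the actual number of older patients already treated and their events on the Section 9.1.5 definition.
- In Section 15.4.2, report the 14-day unacceptable-toxicity percentage for 4-11 and 12-21 years as well as overall.

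This needs no extra patients. The cost is a higher chance of a review pause when the true rate is low, and it should be stated openly:

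| True rate | Remaining seven after m = 5: current | With added count | Whole trial, five older then seven younger, common rate: current | With added count |
|---|---|---|---|---|
| 0.05 | 0.0006 | 0.033 | 0.035 | 0.063 |
| 0.10 | 0.005 | 0.114 | 0.128 | 0.206 |
| 0.15 | 0.019 | 0.224 | - | - |

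At 0.05 and 0.10 the added count alone pauses about as often (0.033 and 0.114) as the original design in Table 5 (0.030 and 0.124). The pause leads to a review and not automatically to termination.

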9.1.5 Definition of Unacceptable Toxicity

Toxicities will be graded according to the NCI CTCAE version 4 criteria. Any Grade 3 or any Grade 4 toxicity that is not reversible within 2 weeks, any life-threatening event deemed related to the study drug, or any treatment-related death will be considered unacceptable.

Any Grade 2 or higher autoimmune toxicities, particularly those affecting vital organs (e.g. cardiac, renal, CNS), will be considered an unacceptable toxicity, if it occurs within 2 weeks post-infusion. Grade 3 or higher surgical complications from insertion of the catheter are considered an unacceptable toxicity.

Exceptions to these unacceptable toxicities are as follows:

- Events associated with the biopsy procedure/catheter placement: Seizures or hemorrhages occurring during anesthesia or the biopsy/catheter insertion proper prior to administration of the agent if Grade 2 or lower.
- Seizures: Due to the nature of the disease under investigation in this protocol, patients may have pre-existing seizures or be susceptible to new seizures as a result of the underlying disease process. Although seizures may be defined as Grade 3 or 4 toxicities under NCI CTC, and will be reported as such in this protocol, seizures will not be considered an unacceptable toxicity if, in the opinion of the site Principal Investigator they have not increased in frequency or can be attributed to another recognized cause of increasing seizure frequency such as sub-therapeutic anti-convulsant levels or biopsy proven tumor progression.
- New or worsening neurologic deficits: Due to the nature of the disease under investigation in this protocol, patients may have an increase in pre-existing neurologic deficits or may develop new neurologic deficits as a result of tumor invasion. A new neurologic deficit, which resolves within 2 weeks after initiation of medical therapy, will not be considered an unacceptable toxicity. New neurological symptoms will not be an unacceptable toxicity if they can be ascribed to tumor progression (e.g. documented with histopathologic analyses of biopsy tissue), or they respond to treatment (e.g. oral steroids) within 2 weeks.

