12 SCREENING AND ON-STUDY TESTS AND PROCEDURES

Table 2. Schedule of Study Tests and Procedures

Description	Within 6 months	Screening: Within 14 days prior to catheter placement	Screening: Within 5 days prior to PVSRIPO	Catheter Placement biopsy, PVSRIPO infusion	After Completion of Infusion	Post infusion (follow-up period) ^a						
Week						0	1	2	4	8	16, 24, 32, 40, 48	
Day		Within 14 days prior to catheter placement	Within 5 days prior to PVSRIPO	0	0	1	7	14	28	56	112, 168, 224, 280, 336	
General Evaluations												
Physical Exam		X	X			X ^b	X	X	X	X		X
Neurologic Exam		X	X			X ^b	X	X	X	X		X
Performance Status		X	X				X	X	X	X		X
Adverse Events ^h	X	X	X			Continuous						
Laboratory Evaluations												
Poliovirus Immunization Booster	X											
CBC w/diff		X				X		X	X	X		X
CMP		X				X		X	X	X		X
PT, aPTT		X										
Serum Pregnancy Test		X	X ^c									
Serum for LSQ and anti-tetanus toxoid IgG	X											
Whole blood for immunologic analysis and/or poliovirus titer (up to 10 mL, except for 4 mL on Day 1 and 6 mL on Day 14)	X	X				X	X	X	X	X	X (at 16 and 24 wks) ^d	
Whole blood for immunologic analysis (not to exceed 3 mL/kg in a 24 hr period or 7 mL/kg in a 8 week period)	X ^e	X ^e					X ^e	X ^e	X ^e	X ^f	X (at 16 and 24 wks) ^{d, f}	
Disease Evaluations												
MRI			X		X ^g (based upon date of enrollment)				X	X		X
CT Scan				X								
Biopsy				X								
Treatment												
PVSRIPO				X								

^a Starting with Day 7 (Week 1), all tests and procedures have a 7-day plus or minus window.

^b Daily after infusion until discharged from hospital

^c Serum pregnancy test, if appropriate, within 48 hours of catheter placement and PVSRIPO

^d At the discretion of the Principal Investigator, an additional blood sample at least 2 years post study drug infusion may be obtained.

^e Whole blood draws for immunologic analysis may be taken (up to 36 mL) at the discretion of the Investigator, but should remain consistent with allowable volumes for pediatric patients depending upon the weight of the child (per Duke policy, the maximum blood volume drawn for research should not exceed 3 mL/kg in a 24 hr period or 7 mL/kg in an 8 week period).

^f At 8, 16, and 24 weeks, up to 76.5 mL of whole blood may be drawn for immunologic analysis (please refer to Duke blood volume policy mentioned above).

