15.9 Sample Size Calculation

A maximum of 12 patients will be treated on this study.

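### Table 4 raises the suspension threshold by patients accrued, not patients assessed; with the 14-day wait removed, Table 5 no longer describes accrual with overlapping assessment windows

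*Combined protocol and SAP*

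**What the plan says.** Section 15.9 sets the size: "A maximum of 12 patients will be treated on this study". Section 15.4.1 gives the acute rule. The event is an unacceptable toxicity in the first 14 days after infusion, and "If the number of patients with an unacceptable toxicity surpasses the noted thresholds, accrual will be suspended". The index column of Table 4 counts the number "of Patients Accrued": at 0-6 the entry is "≥2 patients with unacceptable toxicity", at 7-9 it is "≥3 patients with unacceptable toxicity", and at 10-12 it is four or more. Table 5 gives the suspension probability and expected accrual for true rates of 0.05 to 0.40. It states no assumption about patients whose outcome is still unknown.

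Section 5.5 says the first five patients were spaced at no more than one per 14 days. After a review that found no dose-limiting toxicities, "the protocol was amended to allow for accrual of subsequent patients without the 14-day waiting period in Protocol Amendment 12".

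Two other passages bear on when an outcome is known. One limb of the Section 9.1.5 definition is "Any Grade 3 or any Grade 4 toxicity that is not reversible within 2 weeks". Footnote a of Table 2 reads "Starting with Day 7 (Week 1), all tests and procedures have a 7-day plus or minus window", which allows the Week 2 visit to fall on Day 7.

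**The concern.** The threshold rises at infusion, but the toxicity count catches up only later. While infusions were at least 14 days apart the two largely moved together. Without the wait, a newly infused patient can raise the threshold before contributing any information.

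Suppose eight assessed patients include two toxicities, and patient 9's toxicity is confirmed only after patient 10 has been infused. Three toxicities among nine assessed patients meets the threshold of 3. With ten accrued, the threshold is 4 and accrual continues.

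At stake is whether Table 5 still describes the protection offered by the plan's only quantified rule for acute toxicity, in a trial that now admits children from age 4.

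**Working it through.** **Inputs.** Maximum 12 patients (Section 15.9). Thresholds t = 2 for 0-6, 3 for 7-9 and 4 for 10-12 (Table 4). True rates p from Table 5. First five patients staggered, later ones not (Section 5.5). The number pending when the next patient is infused is not given, so I take a range of 0 to 7 after patient 5.

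**Step 1: reproduce Table 5.** Let P_k(e) be the probability of e toxicities after k patients with no suspension so far. With every outcome known before the next infusion, P_k(e) = (1 - p)·P_{k-1}(e) + p·P_{k-1}(e - 1), and mass reaching e ≥ t(k) leaves as suspended. Expected accrual is Σ k·P(stop at k) + 12·P(no stop).

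| True rate | Table 5: probability / expected N | One at a time |
|---|---|---|
| 0.05 | 0.030 / 11.8 | 0.035 / 11.75 |
| 0.10 | 0.124 / 11.1 | 0.128 / 11.11 |
| 0.15 | 0.262 / 10.2 | 0.259 / 10.21 |
| 0.20 | 0.411 / 9.2 | 0.408 / 9.19 |
| 0.25 | 0.560 / 8.1 | 0.555 / 8.15 |
| 0.30 | 0.681 / 7.2 | 0.686 / 7.15 |
| 0.35 | 0.792 / 6.2 | 0.793 / 6.24 |
| 0.40 | 0.873 / 5.4 | 0.872 / 5.45 |

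Agreement is within about half a percentage point and 0.05 patients. The alternatives tried do not fit. Reading *surpasses* strictly (more than the threshold) gives 0.144 against 0.411 at 0.20. Looks only at 6/9/12 or 3/6/9/12 leave the probabilities unchanged but give expected N of 7.19 or 6.14 against 5.4 at 0.40. So Table 5 rests on ≥ and on one-at-a-time observation.

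**Step 2: allow overlap after patient 5.** With k > 5 accrued and L pending, max(5, k - L) patients are assessed. Their toxicities are compared with t(k), as Table 4 is written. After patient 12 the remaining outcomes are read against 4. All 2^12 outcome sequences are enumerated. Cells show P(threshold ever met) / expected N.

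| True rate | None pending | One pending | All seven pending |
|---|---|---|---|
| 0.10 | 0.128 / 11.1 | 0.098 / 11.3 | 0.091 / 11.3 |
| 0.20 | 0.408 / 9.2 | 0.351 / 9.7 | 0.334 / 9.8 |
| 0.30 | 0.686 / 7.1 | 0.638 / 7.7 | 0.620 / 8.0 |
| 0.40 | 0.872 / 5.4 | 0.846 / 6.0 | 0.836 / 6.3 |

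**Step 3: condition on the reported start.** Assume that no dose-limiting toxicities means 0 unacceptable toxicities in 5, and take p = 0.30. The chance of stopping before patient 12 is infused can be checked by hand.

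- None pending: stop at patient 8 (0.3³ = 0.0270), at 9 (3 × 0.3³ × 0.7 = 0.0567), or at 11 (two events in patients 6-9, then two more: 6 × 0.3² × 0.7² × 0.3² = 0.0238). Total 0.108.
- One pending: patients 6-8 all toxic (0.0270), or four events in patients 6-10 with the one clean patient among 6-8 (3 × 0.3⁴ × 0.7 = 0.0170). Total 0.044.
- Two pending: with 11 accrued only patients 6-9 add information, and all four must be toxic (0.3⁴ = 0.008).
- Three pending: with 11 accrued at most three events (patients 6-8) can be known, and the threshold is 4. The probability is 0, and likewise with more pending.

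The probability of ever meeting the threshold goes from 0.152 (none pending) to 0.133 (one pending) and 0.126 (all seven pending, P(≥4 of 7)). Expected accrual goes from 11.7 to at most 12.0.

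**Step 4: index by assessed patients instead.** The probability of ever crossing returns to 0.128/0.408/0.686/0.872 at 0.10/0.20/0.30/0.40 for any lag. Expected N with two pending is 11.2/9.5/7.5/5.8, still above 11.1/9.2/7.1/5.4. Given 0 of 5 and p = 0.30, the chance of stopping before patient 12 is 0.084 with one or two pending, 0.027 with three and 0 with four or more.

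**The case against.** The strongest reply is that windows may seldom overlap. Section 7.3 reports difficulty enrolling over the first two years. If each infusion follows the previous patient's full assessment, Table 5 stands as the design calculation. The lower age limit may speed accrual, but no rate is given. This stands, and it limits the practical effect.

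The loss is also modest from where the trial now is. Given 0 of 5, the suspension probability at 30% drops by at most 2.6 points and expected accrual rises by at most 0.3 patients. The 0 of 5 result moves the remaining probability away from Table 5 far more than overlap does (0.046 against 0.411 at 20%).

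Detection need not wait for Day 14. Adverse events are captured continuously, examinations are daily until discharge, and serious events reach the sponsor within 24 hours. Several limbs of Section 9.1.5, such as related life-threatening events, need no reversibility wait. Earlier detection shrinks every overlap effect shown above.

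A reader might infer that the trial has lost its acute safeguard. The documents do not support that: the external DSMB-Plus can recommend stopping enrolment (Section 13.7), the study can be ended at any time (Section 9.5), and crossing Table 4 leads to review, not automatic termination. A reader might also blame the removed wait for the fact that two toxicities in patients 6 and 7 would not suspend accrual. That is true even with instant outcomes, because the threshold is 3 from patient 7.

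What remains is that the plan permits overlap, does not say how pending patients count, and prints operating characteristics that assume there are none.

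**Conclusion.** The concern holds in limited form. With overlapping windows, the accrued index makes the rule slower to trigger than Table 5 says: by 5.7 to 7.4 points at a true rate of 20% and 4.8 to 6.6 points at 30%, measured from the reproduced values. Given a clean first five, the change in overall suspension probability is small. The rule's ability to stop accrual before the last patient nearly disappears with two pending, and is nil with three or more.

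These figures assume that a toxicity becomes known only when its assessment closes, that the number pending is constant after patient 5, and, for the conditional figures, that no dose-limiting toxicities means no unacceptable ones. Part of Section 7.3, which the amendment summary says was also edited for the removal of the wait, was not in the text available, so a provision for pending patients cannot be ruled out. This should be fixed, but it does not show that the trial is unsafe.

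**What to change.** 1. Re-head the Table 4 index as the number of patients, taken in order of infusion, whose acute-toxicity outcome is fully assessed. The order matters. If toxicities entered the index at once and clean patients only on completion, a third event after 0 of 5 could be read at 5 + 3 = 8 patients (threshold 3), and with full overlap the suspension probability at 30% could reach P(≥3 of 7) = 0.353 instead of 0.152.
2. Recompute Table 5 for accrual without the wait, above all the expected-number column, which re-indexing alone does not restore. State the assumption about pending patients, and add a version conditional on 0 of 5.
3. Reconcile *surpasses* with ≥; Table 5 matches ≥. Also reconcile the 14-day endpoint with the two-week reversibility clause (an event starting on Day 14 may not be classifiable until Day 14 + 14 = 28) and with the ±7-day window on the Week 2 visit.

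The cost is an amendment, a recomputed table, and a slightly higher chance of a suspension for review when patients overlap: 0.128 against 0.091-0.098 at a true 10% rate. Counting in infusion order can also delay formal counting of a known event while an earlier patient is pending; the DSMB-Plus can act in the meantime.
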